6 STUDY PROCEDURES

6.1 Summary of Procedures

Table 1. Schedule of Study Procedures and Assessments

	Screening	Study Intervention (Weeks 1-3)	Study Intervention (Week 4)	Study Intervention (Weeks 5-7)	Study Intervention (Week 8)	Taper/Bridge	Follow-Up	Early Withdrawal/ Discontinuation
	Day -29 to 0 ¹	Day 1 ¹⁻²¹ (± 1 day)	Day 22-28 (± 3 days)	Day 29-49 (± 1 day)	Day 50-56 (± 3 days)		5 (+ 2) days post final study dose	
Informed consent/assent	X							
Distribution of device for remote HR and BP assessment		X ³						
Demographics	X							
Medical History	X							
Physical Exam	X	X ³						
Weight/height			X		X			
Vital Signs	X	X ³	X		X			
Concomitant Medications of Interest	X		X		X			
ECG	X		X		X			X
Lab assessments	X		X ¹¹					
Pregnancy test ¹³	X							
Blood Collection for PK			X ²		X ²			X ²
Randomization		X ³						
Dose escalation with HR and BP assessment		X ⁴	X ⁴	X ⁴				
Study product administration		X ⁵	X	X	X			
Unmasking					X			X
Study drug taper/bridge						X ⁶		X
Study Diary			Continuous			X ⁶	X ⁶	
CGI-S	X							
CGI-I		X ⁷	X	X ⁷	X			X
ABC	X		X		X			X
asQ Tool ¹²	X		X		X			
Sleep assessments		X ³	X		X			
Safety Events ⁸	X ⁹	X	X	X	X	X	X ¹⁰	X

1 – Day 0 and Day 1 may be the same calendar day.

2 – Preferred sampling: within 60 minutes prior to study product dose or 30-120 minutes after study product dose.

3 – Randomization; distribution of device for remote HR and BP assessment; physical exam, including weight/height; vital signs; and sleep assessments occur only on Day 1 prior to study product administration.

4 – Just prior to dose escalation time point, every 5 (+ 2) days, parent/legal guardian will be asked to measure HR and BP.

5 – Initial dose occurs on Day 1, Day 0 and Day 1 may be the same calendar day. The initial dose will be administered before bedtime on Day 1. Subsequent doses occur according to Section [6.13.1](#).

6 – For GIR arm only. Participants who choose to discontinue GIR will be tapered off study drug at 1 mg every 3 days. Participants who choose to transition to standard of care GIR will continue on up to 7 days of study drug to bridge to standard of care GIR. See Section [6.13.2](#).

7 – Weekly CGI-I, beginning at first weekly telephone assessment.

8 – Includes AEs, SAEs, and safety ESIs, as described in Section [7.1.2](#).

9 – Only AEs directly related to study procedures (e.g., blood collection) during the screening period will be collected.

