6.3 Study Intervention (Day 1 to 56 \pm 3 days)

Day 1 (Day 0 and Day 1 may be the same calendar day):

- Randomization
- Physical exam, including weight and height
- Vital signs, including BP and HR
- Study product administration – single dose at bedtime on Day 1
- Study Diary completion training and provision
- Safety Events, including AEs, SAEs, and safety ESIs; collection of safety events will be initiated after the first study product administration
- Parent/legal guardian-completed sleep assessments (Section 6.9.2)

Weeks 1-3 (Day 1-21 \pm 1 day):

- Study-product administration
- Dose escalation with BP and HR assessment (Section 6.8), prior to dose escalation time point, every 5 (+ 2) days.
- Safety Events, including AEs, SAEs, and safety ESIs

- Study Diary review
- Clinician completed weekly CGI-I, beginning at first weekly telephone assessment (approximately Day 5) (Section **6.9.3**)

Week 4 (Day 22-28 ± 3 days):

- Concomitant medications of interest
- Weight/height
- Vital signs, including HR and BP
- ECG
- Lab assessments for liver toxicity: LFTs
- Blood Collection for PK
- Dose-escalation assessment (Section **6.8**)
- Study-product administration
- Study Diary review
- Clinician-completed CGI-I (Section **6.9.3**)
- Parent/legal guardian-completed ABC (Section **0**)
- Parent/legal guardian-completed sleep assessments (Section **6.9.2**)
- asQ, as appropriate, for participants ≥ 8 years old (Section **6.10**)
- Safety Events, including AEs, SAEs, and safety ESIs

Weeks 5-7 (Day 29-49 ± 1 day):

- Dose-escalation with BP and HR assessment (Section **6.8**), prior to dose escalation time point, every 5 (+ 2) days
- Study-product administration
- Study Diary review
- Clinician-completed weekly CGI-I (Section **6.9.3**)
- Safety Events, including AEs, SAEs, and safety ESIs

Week 8 (Day 50-56 ± 3 days):

- Weight/height
- Vital signs, including HR and BP
- Concomitant medications of interest
- ECG
- Lab assessments for liver toxicity: LFTs, *only if unable to collect at the Week 4 visit*
- Blood Collection for PK
- Study-product administration
- Study Diary review

- Clinician-completed CGI-I (Section [6.9.3](#))
- Parent/legal guardian-completed ABC (Section [0](#))
- Parent/legal guardian-completed sleep assessments (Section [6.9.2](#))
- asQ, as appropriate, for participants \geq 8 years old (Section [6.10](#))
- Safety Events, including AEs, SAEs, and safety ESIs
- Unmasking of participant to determine standard of care plan

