7.1.2 Safety Events of Special Interest (ESIs)

A safety ESI is a select safety event that could be related to the study drug. Safety ESIs will be solicited for their occurrence (No or Yes) at weekly dose-escalation assessments, including in-person assessments (Week 4 and Week 8), and the final telephone safety assessment (5 + 2 days) after the final dose of study drug. The safety ESIs documented will be assessed by the investigator/delegate (defined as a clinician licensed to make a diagnosis) for intensity, causality, and association to provide uniform data collection of all events. Any reported ESIs should be managed, as needed, according to clinical judgement and local guidelines.

Safety ESIs include:

- Syncope/passing out
- Sedation
- Trouble falling asleep
- Trouble staying asleep
- Trouble waking up
- Drowsiness
- Decreased Energy/Fatigue
- Trouble concentrating
- Trouble breathing
- Constipation
- Diarrhea
- Nausea
- Vomiting
- Skin rash
- Itching
- Change in appetite
- Anxious/fearful

- Sadness/depressed mood
- Self-injurious behavior
- Clinically significant hypotension, defined as systolic BP percentile less than the 5th percentile.^{31,34} This corresponds to systolic BP percentiles for neurotypical children under the 8th percentile for males and under the 10th percentile for females.
- Clinically significant bradycardia, defined as HR > 2 SD below mean for age

The following safety ESIs will only be assessed at in-person visits (Week 4 and Week 8):

- Any clinically significant cardiac event (e.g., clinically significant changes on ECG)
- Suicidality via the asQ Tool (see Section [6.10](#))

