7.5 Collection Period and Reporting Procedures

AE information will be gained from direct monitoring of the study participants as well as from clinician observation and self-reporting by the study participants or their guardians. The investigator/delegate (defined as a clinician licensed to make a diagnosis) must document their

assessment of severity and causality in the participant records in a timely manner and submit safety reports as required by their institutional review board (IRB)/research ethics board (REB)/institutional ethics committee (IEC).

AEs, safety ESIs, SAEs and SUSARs will be collected for all participants, following the first study product administration through 5 (+ 2) days after the last study product dose. AEs directly related to study procedures (e.g., blood collection) during the screening period will also be collected.

Safety ESIs will be captured on the Dose Assessment Form electronic case report forms (eCRFs) to provide uniform data collection and will not be reported separately as AEs. As these are expected pre-specified safety ESIs, they will not be reported in an expedited manner but will be reviewed by the MM and the BPCA Data Safety Monitoring Board (DSMB) convened by NICHD and reported to the FDA in the annual report.

Safety ESIs that are associated with any of the criteria that define the event as an SAE will be reported on the AE/SAE CRF set.

Deaths occurring during the study participation, irrespective of causality will be reported on the AE/SAE CRF set.

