10.4.2 Secondary Analysis

Safety profile of GIR will be presented using AEs and solicited safety ESIs. Number of AEs, SAEs, and SUSARS will be summarized by treatment group (GIR vs. placebo) and overall, by severity, and by each Medical Dictionary for Regulatory Activities (MedDRA®) system organ class and preferred term.

Incidence of safety ESIs will also be presented by treatment group (GIR vs. placebo) and overall. Additional model based analyses of safety ESIs will be performed to estimate treatment effect adjusted for baseline covariates and cumulative dose.

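### Safety ESIs are asked about only after dosing starts, with no item-level baseline and no new-or-worsened rule, so pre-existing symptoms can be scored as incident events and dilute the comparison between arms

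*Combined protocol and SAP*

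**What the plan says.** Section 7.1.2 lists the safety ESIs and says that "Safety ESIs will be solicited for their occurrence (No or Yes) at weekly dose-escalation assessments". That covers the Week 4 and Week 8 visits, and the items are asked again at the final safety call. A clinician then rates each reported ESI for intensity and causality.

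Three places fix when collection starts:
- Section 6.3, Day 1: "collection of safety events will be initiated after the first study product administration".
- Section 7.5: "AEs, safety ESIs, SAEs and SUSARs will be collected for all participants, following the first study product administration".
- Table 1, footnote 9 (Section 6.1), on screening: "Only AEs directly related to study procedures (e.g., blood collection) during the screening period will be collected".

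Section 7.5 puts ESIs on the Dose Assessment Form and says that they "will not be reported separately as AEs"; only those meeting a seriousness criterion go to the AE/SAE forms.

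For analysis, Section 10.4.2 says "Incidence of safety ESIs will also be presented by treatment group (GIR vs. placebo) and overall", followed by "Additional model based analyses of safety ESIs will be performed to estimate treatment effect adjusted for baseline covariates and cumulative dose". The baseline covariates are not named. Sections 7.1.2, 7.5, 10.2.2 and 10.4.2 contain no condition that an ESI be new or worse than before treatment.

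**The concern.** Several ESIs describe complaints that a child with Down syndrome and hyperactivity may well have before any study drug. If the question is simply whether the symptom occurred, and it is first asked on treatment, a long-standing symptom and a drug-induced one give the same answer.

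Two things are at stake. The absolute ESI incidences would be too high in both arms as a description of what happens because of treatment. The contrast between arms would also shrink, because children already symptomatic count as events whichever arm they are in. Safety is the only secondary objective (Section 3), ESI incidence is one of its three endpoints, and Section 2.1 says the results may go to the regulator for labelling. Constipation and sedation are listed in Section 2.4.2 as known guanfacine reactions, and when non-serious they reach the analysis through this checklist and not through the AE forms.

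**Working it through.** **1. What exists before the first dose, item by item**

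| ESI | Pre-dose information planned | Same item asked pre-dose? |
|---|---|---|
| Trouble concentrating | Screening ABC, and CGI-S for hyperactivity, inattention and impulsivity; inattention is required at entry (Section 5.2, inclusion 5) | No |
| Constipation | Medical history (Section 6.2) | No |
| Self-injurious behaviour | Medical history; ABC as a general behaviour scale | No |
| Trouble falling asleep, staying asleep, waking up; drowsiness | CSHQ and ESS-CHAD on Day 1 before dosing (Table 1, footnote 3; Section 6.9.2) | No, but overlapping scale scores exist; no text links them to the ESIs |
| Hypotension, bradycardia | BP and HR at screening and Day 1 | Yes, measured |
| ECG change; suicidality | ECG and asQ at screening (asQ from age 8, where the child is able) | Yes |

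The gap is therefore real for part of the list, not all of it.

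**2. Effect on the comparison**

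The documents give no ESI rate, baseline prevalence or power, so there is no planned figure to reproduce. Read incidence as the proportion of children with at least one Yes. Let b be the proportion symptomatic before dosing (equal in expectation across arms by randomization) and p the new-onset risk in the others. If every pre-existing symptom is scored Yes:

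- observed incidence = b + (1 − b)p
- observed difference = (1 − b)(p_GIR − p_placebo)

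The difference keeps its sign and is zero when the true difference is zero. It is only scaled down.

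With assumed new onset of 35% on GIR and 15% on placebo (difference 20 points, ratio 35/15 = 2.33):

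| b | GIR | Placebo | Difference | Ratio |
|---|---|---|---|---|
| 10% | 0.10 + 0.90×0.35 = 41.5% | 0.10 + 0.90×0.15 = 23.5% | 18 points | 1.77 |
| 30% | 0.30 + 0.70×0.35 = 54.5% | 0.30 + 0.70×0.15 = 40.5% | 14 points | 1.35 |
| 50% | 67.5% | 57.5% | 10 points | 1.17 |
| 70% | 80.5% | 74.5% | 6 points | 1.08 |

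If only a share s of the pre-existing symptoms is scored Yes, and the remaining children carry the same risk p, b is replaced by s×b. For example, b = 50% and s = 0.5 gives (1 − 0.25)×20 = 15 points.

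**3. What that means with this sample**

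Sixty children at 2:1 is 40 and 20 (Sections 5.1 and 4.2.1). The table assumes 40% against 10% new onset and a two-sided 5% test. Power is by normal approximation, with the Fisher exact value in brackets.

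| b | Any Yes | Power, any Yes | At risk if symptom-free only | Power, new onset only |
|---|---|---|---|---|
| 0% | 40% v 10% | 70% (67%) | 40 v 20 | 70% (67%) |
| 20% | 52% v 28% | 42% (35%) | 32 v 16 | 59% (53%) |
| 30% | 58% v 37% | 33% (25%) | 28 v 14 | 52% (51%) |
| 50% | 70% v 55% | 21% (18%) | 20 v 10 | 37% (30%) |

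At b = 30% the ratio falls from 4.0 to 1.57. Other assumed pairs at b = 30% behave alike by normal approximation: 30% v 5% gives 24% (any Yes) against 45% (new onset only), and 50% v 15% gives 44% against 61%.

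There is a limit. At b = 70% in the 40% v 10% case, only 12 and 6 children are symptom-free, and exact power is 9.0% for new onset against 9.8% for any Yes. Restricting to new onset alone gains nothing there, so worsening must also count.

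**The case against.** The strongest reply has four parts.

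- **Baselines exist.** A reader might infer that no ESI can be compared with its pre-dose state, sleep included. The documents do not support that. CSHQ and ESS-CHAD are completed before the first dose and again at Weeks 4 and 8, and Section 10.4.3 plans models of both. HR, BP, ECG and asQ have baselines, and CGI-S and ABC describe inattention and behaviour at entry. This stands, and it narrows the point. But scale totals do not supply an item-level Yes or No, and nothing ties them to the ESI table.
- **Counting pre-existing symptoms is an inference.** A reader might say the plan counts them, or that weekly asking makes it nearly certain. The documents say neither. The Dose Assessment Form is not shown, some items (change in appetite, decreased energy) are worded as change, and a clinician reviews each ESI. This also stands. What remains is that no rule excludes them, so sites may score the same chronic symptom differently, although Section 7.1.2 aims at uniform collection.
- **The analysis is not raw incidence alone.** Section 10.4.2 adds a covariate-adjusted model, and Section 10.4 defers detail to a SAP before data lock. A definition could still be written there. Item-level baseline status cannot be added at that stage, because it will not have been collected.
- **Placebo protects the comparison.** A reader might infer that the signal is masked. Randomization keeps the contrast fair; the harm is attenuation. The objective is descriptive and no ESI power is claimed.

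**Conclusion.** The point holds as a gap in baseline and definition for part of the ESI list, clearest for trouble concentrating, constipation and self-injurious behaviour. Absolute incidences can be inflated in both arms, and the risk difference is multiplied by (1 − b). Under the assumed 35% v 15%, that leaves 14, 10 or 6 of 20 points at b = 30%, 50% or 70%, and 18 points at b = 10%.

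The size rests on three assumptions that the documents do not settle: the prevalence b, the new-onset risks, and that every pre-existing symptom is scored Yes. The direction, dilution toward no difference, needs only that some pre-existing symptoms are scored. It does not create a false difference between arms. It deserves correction because the remedy is cheap and the missing answers cannot be recovered once a child has been dosed.

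**What to change.** 1. Add the same ESI checklist, with intensity, on Day 1 before the first dose (Table 1 and Section 6.3), and state in Section 7.5 that these answers are baseline values and not safety events.
2. In Section 10.4.2, define the ESI endpoint as new or worsened in intensity since Day 1, and keep the all-occurrence table as supportive.
3. Name baseline ESI status as a covariate in the planned ESI model.

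The cost is one short extra checklist for families and sites at an existing visit, one copy of an eCRF page and one definition. Dosing and clinical management do not change.

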7.2 Guidelines for Determining Seriousness

A **serious adverse event** (SAE) or **serious suspected adverse reaction** or **serious adverse reaction or serious event of special interest** as determined by the investigator or the sponsor is any event that results in any of the following outcomes:

- Death
- Life-threatening AE (“life-threatening” means that the study participant was, in the opinion of the investigator or sponsor, at immediate risk of death from the reaction as it occurred and required immediate intervention)
- Persistent or significant incapacity or substantial disruption of the ability to conduct normal life functions
- Inpatient hospitalization or prolongation of existing hospitalization
- Congenital anomaly or birth defect
- Important medical event that may not result in one of the above outcomes, but may jeopardize the health of the study participant or require medical or surgical intervention to prevent one of the outcomes listed in the above definition of serious event

7.3 Guidelines for Assessing Intensity

The investigator/delegate (defined as a clinician licensed to make a diagnosis) will use the following definitions when assessing intensity of an event:

- **Mild** - Participant is aware of symptoms or has minor findings but tolerates them well, and no or minimal intervention required
- **Moderate** - Participant experiences enough symptoms or findings to require intervention
- **Severe** - Participant experiences symptoms or findings that require significant intervention

7.4 Guidelines for Assessing Causality

The investigator/delegate (defined as a clinician licensed to make a diagnosis) will use the following question when assessing causality of an event to study drug: Is there a reasonable possibility that the drug caused the event? “Reasonable possibility” means that there is evidence to suggest a causal relationship between the study drug and the AE. An affirmative answer designates the event as a SAR.

7.5 Collection Period and Reporting Procedures

AE information will be gained from direct monitoring of the study participants as well as from clinician observation and self-reporting by the study participants or their guardians. The investigator/delegate (defined as a clinician licensed to make a diagnosis) must document their

assessment of severity and causality in the participant records in a timely manner and submit safety reports as required by their institutional review board (IRB)/research ethics board (REB)/institutional ethics committee (IEC).

AEs, safety ESIs, SAEs and SUSARs will be collected for all participants, following the first study product administration through 5 (+ 2) days after the last study product dose. AEs directly related to study procedures (e.g., blood collection) during the screening period will also be collected.

Safety ESIs will be captured on the Dose Assessment Form electronic case report forms (eCRFs) to provide uniform data collection and will not be reported separately as AEs. As these are expected pre-specified safety ESIs, they will not be reported in an expedited manner but will be reviewed by the MM and the BPCA Data Safety Monitoring Board (DSMB) convened by NICHD and reported to the FDA in the annual report.

Safety ESIs that are associated with any of the criteria that define the event as an SAE will be reported on the AE/SAE CRF set.

Deaths occurring during the study participation, irrespective of causality will be reported on the AE/SAE CRF set.

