7 ASSESSMENT OF SAFETY

7.1 Adverse Events

An **adverse event (AE)** is any untoward medical occurrence in humans, whether or not considered drug-related, which occurs during the conduct of a clinical trial. Any change in clinical status, ECGs, routine labs, x-rays, physical examinations, etc. that is considered clinically significant by the study investigator is considered an AE.

A **suspected adverse reaction (SAR)** is any AE for which there is a reasonable possibility that the drug caused the event. A reasonable possibility implies that there is evidence that the drug caused the event. An **adverse reaction** is any AE caused by the drug.

A **serious, unexpected, suspected adverse reaction (SUSAR)** is defined as a SAR that is both serious and unexpected for which a reasonable causal relationship with the drug use is suspected but not confirmed.

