10.2.2 Secondary Endpoints

The following safety endpoints will be collected throughout the Week-8 treatment period of the study:

- Incidence of SAEs
- Incidence of safety ESIs
- Incidence of AEs

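### Non-serious ESIs meet the protocol's AE definition but are kept off the AE record, so AE incidence read alone is understated and no table counts children with any event

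*Combined protocol and SAP*

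**What the plan says.** - **Definition (Section 7.1).** An AE "is any untoward medical occurrence in humans, whether or not considered drug-related, which occurs during the conduct of a clinical trial". There is no exception for ESIs. The same section counts an ECG change as an AE when the investigator judges it clinically significant.
- **ESI list (Section 7.1.2).** ESIs are asked about as No or Yes at the weekly dose assessments, and each is assessed for intensity and causality. The list includes sedation, drowsiness, constipation, nausea, hypotension and bradycardia beyond stated thresholds, and clinically significant ECG changes.
- **Recording rule (Section 7.5).** ESIs are captured on the Dose Assessment Form and "will not be reported separately as AEs". The exception is for serious events: "Safety ESIs that are associated with any of the criteria that define the event as an SAE will be reported on the AE/SAE CRF set".
- **Endpoints (Section 10.2.2).** "Incidence of safety ESIs" and "Incidence of AEs" are listed as separate secondary safety endpoints.
- **Analysis (Section 10.4.2).** "Number of AEs, SAEs, and SUSARS will be summarized by treatment group", with breakdowns by severity and by MedDRA system organ class and preferred term (SOC/PT). ESI incidence is to be shown by arm and overall, and modelled for a treatment effect. No MedDRA mapping of ESIs, no ESI table by intensity and no combined AE-plus-ESI summary is described.

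**The concern.** The AE endpoint does not match the protocol's own definition of an AE. A non-serious ECG change judged clinically significant is an AE under Section 7.1, but under Sections 7.1.2 and 7.5 it is an ESI that is not recorded as an AE. The same holds for every non-serious untoward event on the ESI list.

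Characterising safety is the trial's only secondary objective (Section 3), and Section 2.1 says the results may go to the FDA for labelling. An AE percentage will naturally be read as covering all untoward events. Here it would leave out several reactions that the protocol itself attributes to guanfacine. Because the diverted terms include known drug effects, a comparison of AE incidence between arms would plausibly be pulled toward no difference. That is an expectation, since the documents give no rates by arm.

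**Working it through.** The plan states no AE or ESI rate, so there is no figure to reproduce. The check is a reading of the text, a count of overlap, and an illustration under assumed rates.

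**1. Which events are diverted.** Section 7.1.2 lists 21 ESIs assessed throughout and 2 assessed only in person: 21 + 2 = 23. Under Section 7.5 their non-serious occurrences stay on the Dose Assessment Form; serious ones go on the AE/SAE forms.

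**2. Overlap with the reactions in Section 2.4.2 (8 listed).**

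| Reaction | Matching ESI |
|---|---|
| Sedation | Yes |
| Constipation | Yes |
| Decreased heart rate | Yes, if more than 2 SD below the mean for age |
| Decreased blood pressure | Yes, if systolic is below the 5th percentile |
| Weakness | Only if matched to Decreased Energy/Fatigue |
| Dry mouth, dizziness, impotence | No |

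Strict match: 4 of 8. Broad match: 5 of 8.

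**3. Overlap with the post-marketing events above 1% in Section 2.1.2 (6 listed).** Somnolence, fatigue and nausea match; dry mouth, dizziness and headache do not: 3 of 6. The two lists together hold 11 distinct reactions, of which 6 (strict) or 7 (broad) match, or 55% to 64%.

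**4. Possible size of the gap (assumed rates).** Let e be the proportion of children with at least one non-serious ESI and o the proportion with at least one other AE. The AE table shows o. If the two are independent:

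- any event = 1 − (1 − e)(1 − o)
- gap = any event − o = e(1 − o)

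| e | o (AE table) | Any AE or ESI | Gap (percentage points) |
|---|---|---|---|
| 30% | 60% | 72% | 12 |
| 30% | 20% | 44% | 24 |
| 50% | 40% | 70% | 30 |
| 70% | 60% | 88% | 28 |
| 70% | 20% | 76% | 56 |

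Over e = 30–70% and o = 20–60%, the gap runs from 12 to 56 points.

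**5. Why the two tables cannot be added.** One child can appear in both. Without assuming independence, the proportion with any event lies between max(e, o) and min(100%, e + o). With e = 50% and o = 40%, that is anywhere from 50% to 90%. Only a count per child across both records settles it.

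**The case against.** The strongest reply is that Section 7.5 is a rule about data entry. Not reporting an ESI separately as an AE may mean only that the same event is not entered on two forms, and nothing in Section 10 says ESIs are excluded from AE incidence at analysis. Section 10.4 also leaves detailed methods to a SAP due before data lock. It is true that the plan does not settle this expressly. But nothing says that ESIs are added back, and Section 10.4.2 names AEs, SAEs and SUSARs for the severity and MedDRA tables and handles ESIs separately. On the plain reading, the omission follows from a stated rule.

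The second reply is that these events get more attention than ordinary AEs: weekly solicitation, grading, their own endpoint, display by arm and a model. This stands, and it limits the consequence. It does not supply a count of children with any event.

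The third reply concerns the remedy. The ESI list includes trouble concentrating and sleep difficulties in children enrolled for inattention and hyperactivity. The list is not solicited before the first dose, and Table 1 limits screening events to procedure-related AEs. Some positive answers may therefore reflect symptoms already present, and a combined figure could run high in both arms and hide a difference. This also stands. It is the reason to add a combined table and not to redefine the AE endpoint.

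**Conclusion.** The point holds as a reporting defect that should be corrected. Non-serious ESIs fall within the AE definition but outside the AE record, so AE incidence and its severity and MedDRA breakdowns are understated when read alone. The extent is 4 of the 8 reactions in Section 2.4.2, or 5 with the broad match for weakness. The range of 12 to 56 percentage points rests entirely on assumed rates and independence and is not a prediction.

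A reader might infer more than the documents support:

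- **That these reactions disappear from the safety results.** They do not, because ESI incidence is reported by arm and modelled.
- **That all ESIs are shut out of the AE record.** Those meeting an SAE criterion go on the AE/SAE forms.
- **That most known reactions are diverted.** On a strict match to Section 2.4.2 it is exactly half. Heart rate or blood pressure changes short of the ESI thresholds remain AEs if judged clinically significant.
- **That the AE rate will be most wrong in the guanfacine arm, or unusable for labelling or for comparison with other trials.** The documents contain no rates that could show this.

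**What to change.** In Section 10.4.2 and the SAP:

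1. Keep the separate AE and ESI tables, and title the first *AEs other than non-serious pre-specified ESIs*, so that its scope is plain.
2. Map ESIs to MedDRA terms.
3. Show ESIs by the intensity already collected.
4. Add a table of the number and percentage of children with at least one AE or ESI, by arm, SOC/PT and maximum intensity. Percentages matter because 2:1 allocation of 60 children gives about 40 and 20, so equal rates would produce twice the count in the guanfacine arm.
5. Note beside that table that ESIs are solicited without a pre-dose solicitation, so the combined figure may include pre-existing symptoms. It supplements the separate tables and does not replace them.

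The cost is some coding work and two added displays. Most ESI terms are fixed, but the cardiac item is open-ended and the appetite item has no direction, so those need a stated mapping rule. No new data and no change to site procedures are needed.
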